4.1.2. Exposed Set of subjects with a negative RSV exposure status

The Exposed Set of subjects with a negative RSV exposure status will include all vaccinated subjects assessed as RSV unexposed at screening based on in-stream baseline serological testing

The safety analysis of incidence of RSV-LRTI will be conducted on the cohort of subjects with a negative RSV exposure status (at screening based on in-stream baseline serological testing) as well as on the entire ES.

4.1.3. Per-protocol Set for analysis of immunogenicity

The per-protocol set (PPS) cohort for analysis of immunogenicity will be defined by timepoint (Day 31, Day 61 and End of the first RSV transmission season) and will consist of all subjects from the ES who complied with eligibility criteria, study procedures up to the end of the study and had immunogenicity results in the epoch as described below,

More specifically, the PPS cohort for analysis of immunogenicity for specific timepoint (Day 31 [Visit 3], Day 61 [Visit 5] and at end of the first RSV transmission season [Visit 7]) will include all evaluable subjects:

- Who met all eligibility criteria (i.e., no protocol violation linked to the inclusion/exclusion criteria, including age).
- Who received study vaccine as scheduled per protocol.
- For whom the administration route and site of the vaccine was as according to protocol.
- Who received the vaccine according to protocol procedures.
- Who complied with the vaccination schedule, as specified Table 4 in of the SAP.
- Who did not receive a concomitant medication/product/vaccine leading to exclusion from a PPS analysis, as described in Section 7.6.2 of the protocol, up to Day 31 (Visit 3)/up to Day 61 (Visit 5) /at Visit 7 (end of the first RSV transmission season).
- Who complied with the timings of the post vaccination blood sampling for immune response evaluation, up to Day 31 (Visit 3)/up to Day 61 (Visit 5) /at Visit 7 (end of the first RSV transmission season), as specified in Table 4 of the SAP.

When presenting different time-points, the PPS for immunogenicity will be adapted for each time-point (Day 31, Day 61 and End of first RSV transmission season).

Table 4 presents the intervals between study visits that determine subjects' eligibility for inclusion in the PPS analysis.

Table 4 Maximum allowed interval between study visits for PPS

Interval	Allowed length of interval ¹
Visit 1 (Day 1) → Visit 3 (Day 31)	23 - 44 days
Visit 1 (Day 1) → Visit 5 (Day 61)	60 - 81 days
Visit 3 (Day 31) → Visit 5 (Day 61)	28 - 37 days ²
Visit 5 (Day 61) → Visit 7 (end of the first RSV transmission season)	90 days to the defined end of transmission season or up to 4 weeks after

¹ Subjects will not be eligible for inclusion in the PP cohort for analysis of immunogenicity if they make the study visit outside this interval.

² The interval between Visit 1 and Visit 5 must be a minimum of 60 days to be in line with the active comparator vaccination schedules as per the respective approved labels.

4.2. Criteria for eliminating data from Analysis Sets

Elimination codes are used to identify subjects to be eliminated from analysis. Detail is provided below for each set.

4.2.1. Elimination from Exposed Set (ES)

Code 1030 (Study vaccine not administered at all), code 900 (invalid informed consent) and code 800 (fraudulent data) will be used for identifying subjects eliminated from ES.

4.2.2. Elimination from Exposed Set (ES) subjects with a negative RSV exposure status

Code 1030 (Study vaccine not administered at all), code 900 (invalid informed consent) and code 800 (fraudulent data) will be used for identifying subjects eliminated from ES. Additionally, code 2020 (RSV- seropositive antibody status at baseline) will be used to identify all the subject with negative RSV exposure status.

4.2.3. Elimination from Per-protocol analysis Set (PPS)

4.2.3.1. Excluded subjects

A subject will be excluded from the PPS analysis under the following conditions

For codes 1040, 1070, 1080, 1090, 2040, 2060, 2070, 2080: subjects will be eliminated from a specific visit (at which the condition is met) onwards.

For codes 2090, 2100, 2120: subjects will be eliminated at the specific visit at which the condition is met

Code	Condition under which the code is used	Visit (timepoints) where the code is applicable	Applicable for analysis set
800	Fraudulent data	All	All
900	Invalid informed consent	All	all
1030	Study vaccine not administered at all	All	Safety, immunology
1040	Administration of concomitant vaccine(s) forbidden in the protocol:- 
 • Any investigational or non-registered product (drug or vaccine) other than the study vaccines used during the study period • A vaccine not foreseen by the study protocol administered during the period starting 30 days before the first dose and ending 30 days after the last dose of vaccine*, with the exception of: 
 – Scheduled routine pediatric vaccines which may be administered \geq 7 days before a dose and \geq 7 days after a dose of study vaccines, with the exception of live viral vaccines which may be administered 	Visit 3,5, 7	Immunogenicity

Code	Condition under which the code is used	Visit (timepoints) where the code is applicable	Applicable for analysis set
	≥ 14 days before a dose or ≥ 7 days after a dose. – Vaccines needed for urgent individual medical need (e.g., rabies prophylaxis)		
1050	Randomisation failure	All	Immunogenicity
1060	Randomisation code was broken	All	Immunogenicity
1070	Subjects got vaccinated with the correct vaccine but containing a lower volume	All	Immunogenicity
1070	Vaccination not according to protocol: 
Wrong replacement or study vaccine administered (not compatible with the vaccine regimen associated to the treatment number)Site or route of study vaccine administration wrong or unknownAdministration not according to protocol for reason specified by the investigator, other than side, site and route	All	Immunogenicity
1080	Vaccine temperature deviation (vaccine administered despite a Good Manufacturing Practices (GMP) no-go temperature deviation for RSV vaccines only)	All	Immunogenicity
1090	Expired vaccine administered (only applicable for RSV vaccine)	All	Immunogenicity
2010	Protocol violation (inclusion/exclusion criteria including age)	All	Immunogenicity
2040	Administration of any medication forbidden by the protocol: 
Any investigational or non-registered product (drug) other than the study vaccines used during the study periodLong-acting immune-modifying drugs administered at any time during the study periodImmunosuppressants or other immune-modifying drugs administered chronically (i.e., more than 14 days in total) during the study periodImmunoglobulins and/or any blood products administered during the study period	Visit 3, 5, 7	Immunogenicity
2050	Underlying medical condition forbidden by the protocol	Visit 3, 5, 7	Immunogenicity
2060	Intercurrent medical condition → Intercurrent medical condition that has the capability of altering immune response, or alteration of initial immune status (suspected or confirmed immunosuppressive or immunodeficient condition) which may influence immune response	Visit 3, 5, 7	Immunogenicity
2070	Concomitant infection not related to the vaccine which may influence immune response	Visit 3, 5, 7	Immunogenicity
2080	Subjects did not comply with vaccination schedule:- Number of days between dose 1 and dose 2 is outside [23-44 days]	Visit 3	Immunogenicity

Code	Condition under which the code is used	Visit (timepoints) where the code is applicable	Applicable for analysis set
2090	Subjects did not comply with blood sample schedule 
 Number of days between dose 1 and visit 3 blood sample is outside [23-44 days] Number of days between dose 1 and visit 5 blood sample is outside [60-81 days] Number of days between dose 2 and visit 5 blood sample is outside [28-37 days] for RSV 2D group Number of days between visit 5 blood sample and visit 7 blood sample is outside [92-148 days] 	Visit 3, 5, 7	Immunogenicity
2100	Serological results not available post-vaccination:- No immunological result at visit x for all 2 tests - RSV A Neutralising antibody titer and RSVPreF3-specific IgG antibody concentration	Visit 3, 5 and 7	Immunogenicity
2120	Obvious incoherence or abnormality or error in data :- Incoherence between CRF and results, wrong sample labelling, Central/internal/external lab deviations; incorrect spinning/processing of sample including processing within the time required by protocol; temperature deviations from range defined in protocol and/or SPM - room temperature/refrigerator/freezer; an assessment was completed but was not completed according to protocol or SPM.	Visit 3, 5, 7	Immunogenicity

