ChAd155-RSV: Chimpanzee Adenovirus Type 155 RSV vaccine; **FB:** Formulation buffer S9b; **RSV ChAd:** ChAd155-RSV vaccine; **1D:** 1 Dose (1.5x10¹⁰ vp/dose); **2D:** 2 Dose (5x10¹⁰ vp/dose).

- Controls: active comparator vaccines (*Bexsero*, or *Nimenrix*, or *Synflorix*, or *Menveo*, or Placebo (FB)*).
 - * The choice of active comparator vaccine (*Bexsero*, *Nimenrix*, *Synflorix*, or *Menveo*) or Placebo is done at the country level. Refer to the ICF for the local choice of comparator/Placebo.
- Vaccination schedules:
 - **RSV investigational vaccine:** In the 1 Dose (1D) groups, a single lower dose of 1.5x10¹⁰ vp will be administered IM at Day 1 (Visit 1). Formulation buffer will be administered in the 1D groups at Day 31 (Visit 3). In the 2 Dose (2D) groups, two doses of 5x10¹⁰ vp will be administered IM according to a 0, 1-month schedule, (i.e., at Day 1 [Visit 1] and Day 31 [Visit 3]) (see Figure 1 and Table 1). Dose 1 will be administered before the first RSV season and the second dose will be given one month after the first dose (RSV seasons will be determined for each country based on local epidemiological data and documented in the Study Procedures Manual [SPM]. The RSV season is defined as the period of the year when 70% of the RSV cases have occurred in previous years. For the calculation, where available, data from up to the ten previous years should be applied. If the data permit calculation of the actual date of the beginning of the season, rather than approximation to the nearest month, this is desirable.)
 - **Comparator or Placebo:** In countries where *Bexsero* or *Nimenrix* is used as a control, two doses will be administered IM with at least a 2-month interval between these primary doses. A booster dose will be administered IM in the second year of life at Visit 7, with an interval of at least 2 months between the

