- In countries where Placebo is used as a control, one dose will be administered IM at Day 31 (Visit 3) in the 1D RSV + Placebo group and two IM doses will be administered IM according to a 0, 1-month schedule at Day 1 (Visit 1) and Day 31 (Visit 3) in the Placebo group (see Figure 1 and Table 1).
- Treatment allocation: infants will be randomized using a centralized randomization system on internet (SBIR) before first vaccination and after assessment of eligibility (i.e., after screening conclusion) (refer to Section 6.2.2 of the protocol for details about randomization of treatment). The randomization algorithm will use a minimization procedure accounting for country as a minimization factor and the grouping comparator/placebo as a stratification factor.
- Blinding: not applicable for Epoch 001 (Screening Visit), observer-blind in Epoch 002 and single-blind in Epoch 003 and Epoch 004. Refer to Section 6.3 of the protocol for details of blinding procedure.

- Blinding of study epochs

Study Epochs	Blinding
Epoch 001	N/A
Epoch 002	observer-blind
Epoch 003	single-blind
Epoch 004	single-blind

- Sampling schedule:

- Blood samples for **hematology/biochemistry** will be taken from all infants at Screening (up to 30 days before first vaccination to Day -1). Blood samples for **hematology/biochemistry** may be taken from infants at any timepoints, if deemed necessary by the investigator. Refer to Table 12 of the protocol for the list of parameters to be tested.
- Refer to Section 6.6.1.2.2 and Figure 2 of the protocol for information about the re-testing of samples in case of any Grade 1 abnormality with potential clinical relevance (according to investigators judgment) or any \geq Grade 2 abnormality.
- Blood samples for **humoral immunogenicity** will be taken from all subjects at Screening and on Day 31, Day 61, and at the visit occurring at the end of the first RSV transmission season.
- Blood sample for **assessment of mechanism of illness (potential ERD)** will be taken from subjects hospitalized for LRTI (only for RSV-positive subjects using a locally available RSV test).
- Nasal swab: there will be monthly nasal swab to detect asymptomatic RSV infections during the RSV season and if following active or a passive surveillance contacts, a subject present symptoms of RTI, a nasal swab will be collected (as well as a sample for local testing i.e., the type of sample to be determined locally [e.g., swab, etc.]) (Refer to the SPM).

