3.2.2. Secondary endpoints

- Occurrence of RSV-RTI, RSV-LRTI, severe RSV-LRTI and very severe RSV-LRTI (according to standardized case definitions) as from first vaccination (Day 1) up to the end of the first RSV transmission seasons.
- Occurrence of RSV-RTI, RSV-LRTI, severe RSV-LRTI and very severe RSV-LRTI (according to standardized case definitions) as from first vaccination (Day 1) up to the end of the second RSV transmission seasons.
- Occurrence of SAEs from first vaccination (Day 1) up to the end of the second RSV transmission seasons.
- Occurrence of RSV-LRTI (AE of special interest) as from first vaccination (Day 1) up to the end of the first RSV transmission season, and up to the end of the second RSV transmission seasons.

- Occurrence of very severe RSV-LRTI (according to standardized case definitions) among RSV infected infants with a negative RSV exposure status (at screening based on in-stream baseline serological testing) from first vaccination (Day 1) up to the end of the first RSV transmission seasons.
- Humoral response to the investigational RSV vaccine, pre-vaccination (Screening), post-Dose 1 (Day 31) and post-Dose 2 (Day 61 and at the end of the first RSV transmission season):
 - Neutralizing antibody titers against RSV-A
 - RSV F antibody concentrations

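### Dosing-deviation codes start per-protocol elimination one sample too early: a Dose 2 deviation at Visit 3 removes the Day 31 post-Dose 1 result from the Day 31 PPS

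*SAP*

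**What the plan says.** SAP section 4.2.3.1 has two rules for when elimination from the immunogenicity PPS begins.

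- For a list of codes that includes 1070 (vaccination not according to protocol, including low volume), 1080 (temperature deviation), 1090 (expired product) and 2080 (dose interval), "subjects will be eliminated from a specific visit (at which the condition is met) onwards".
- For the codes that describe the sample or its result, elimination is confined to one visit: "For codes 2090, 2100, 2120: subjects will be eliminated at the specific visit at which the condition is met".

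Code 1070 has no product restriction. Codes 1080 and 1090 are limited to RSV vaccine; for 1090 the wording is "Expired vaccine administered (only applicable for RSV vaccine"). Code 2080 reads "Number of days between dose 1 and dose 2 is outside [23-44 days"], is not limited to an arm, and has Visit 3 alone in its visit column.

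Section 2 places the two RSV injections of the 2D groups "at Day 1 [Visit 1] and Day 31 [Visit 3"]. For the other RSV arm, "Formulation buffer will be administered in the 1D groups at Day 31 (Visit 3"). The humoral immunogenicity samples "will be taken from all subjects at Screening and on Day 31, Day 61" and at the end of the first season. Section 3.2.2 labels those samples "post-Dose 1 (Day 31) and post-Dose 2 (Day 61 and at the end of the first RSV transmission season"). Section 4.1.3 equates the Day 31 PPS with Visit 3, and section 5.2.1 presents Day 31 results on that set.

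**The concern.** A rule that begins at the visit of the deviation suits a fault in the sample. It does not suit a fault in an injection given at the same visit as the sample, because that injection can only influence later samples. Visit 3 carries both Dose 2 and the sample that measures Dose 1, so the written rule makes membership of the Day 31 PPS depend partly on how Dose 2 was given.

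Section 8 explains that a separate Day 31 PPS was introduced in the SAP, whereas the protocol used the Day 61 set for Day 31 results. Tying the new set to Dose 2 brings back part of the dependence that this change removed. At stake are valid Day 31 results in the primary immunogenicity analysis set, and so some precision in the Day 31 geometric means.

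**Working it through.** The SAP states no figure for this point, so there is none to reproduce. The check is a tabulation of the rule, followed by simple arithmetic on size.

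**Step 1: timepoints removed, by visit of the deviation.** PPS timepoints are Visit 3 (Day 31), Visit 5 (Day 61) and Visit 7 (end of first season), from section 4.1.3.

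| Deviation at | Rule as written removes | First-later-sample rule removes | Difference |
|---|---|---|---|
| Visit 1 | V3, V5, V7 | V3, V5, V7 | none |
| Visit 3 | V3, V5, V7 | V5, V7 | Day 31 kept |
| Visit 5 | V5, V7 | V7 | Day 61 kept |
| Visit 7 | V7 | none | end of season kept |

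The Visit 3 row follows directly from the SAP, because the Day 31 result is labelled post-Dose 1. The Visit 5 and Visit 7 rows concern code 1070 for comparator injections. They hold only if blood is drawn before the injection, an order the SAP does not state.

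**Step 2: which arms are exposed at Visit 3.** Table 1 lists 15 sub-groups. At Visit 3 the five 2D sub-groups receive RSV vaccine and the five 1D sub-groups receive buffer. Among the controls, the Bexsero, Nimenrix and Placebo groups receive buffer, and the Synflorix and Menveo groups receive their vaccine.

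- Codes 1080 and 1090 (RSV vaccine only) can be met at Visit 3, as scheduled, in 5 of 15 sub-groups, all of them 2D.
- Codes 1070 and 2080 can be met in any arm.

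**Step 3: what code 2080 adds to code 2090.** Both use 23 to 44 days from Dose 1: code 2080 for Dose 2, code 2090 for the Visit 3 sample.

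- Sample and Dose 2 on the same day, out of window: code 2090 already removes Day 31, and 2080 adds nothing at that timepoint.
- Sample in window, Dose 2 on another day out of window: 2090 does not apply, and 2080 removes a Day 31 result that is otherwise valid.

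Only the second case is an extra loss.

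**Step 4: does any other text move the start of elimination?** No. In section 4.1.3 the conditions on concomitant products and on sampling times carry a timepoint, but the conditions on receiving vaccine per protocol do not. Sections 5.2.1 and 8 are silent on it.

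**Step 5: size.** The target is 50 infants per pooled group (Table 2). The number affected, k, is an assumption, since the SAP gives no deviation counts. With the same standard deviation on the log scale, and ignoring the small change in the t quantile, interval width scales as sqrt(50/(50 − k)):

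- k = 1: sqrt(50/49) = 1.010, about 1% wider
- k = 3: sqrt(50/47) = 1.031, about 3% wider
- k = 5: sqrt(50/45) = 1.054, about 5% wider

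Section 5.2.1 calls for a second analysis on the Exposed Set when more than 10% of vaccinated subjects with serology are excluded in any group. With all 50 having serology, 5/50 = 10% does not exceed that threshold and 6/50 = 12% does.

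**The case against.** The strongest reply is that little hangs on this. Immunogenicity is a secondary objective, and section 5.2.1.1 plans only within-group description; no between-group immunogenicity contrast is specified. An excluded result leaves the Day 31 PPS but stays in the Exposed Set. Section 4.1.1 foresees an immunogenicity analysis on that set, section 5.2.1 requires one above the 10% threshold, and section 5.2.1.1.1 adds one on the RSV-unexposed part of it. Reaching five infants through codes 1080 and 1090 alone would mean that 10% of RSV 2D received expired or temperature-compromised product at Dose 2. All of this stands and sets the severity at minor.

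A reader might also infer three stronger things that the SAP does not support.

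- **Illness-related selection that differs between dose groups.** This joins two mechanisms. Deferral of Dose 2 falls under code 2080, which applies in every arm, and every arm has an injection at Visit 3. The codes confined to RSV 2D concern product handling, which nothing in the SAP links to an infant's illness or titre. No single code does both.
- **Loss of precision in RSV 2D only.** That is true of codes 1080 and 1090 at Visit 3, but not of 1070 or 2080.
- **Any late Dose 2 costs a valid Day 31 result.** When sample and dose fall on the same day, code 2090 already removes the result, and changing 2080 restores nothing.

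The reply does not remove the defect itself. Read literally, the rule excludes from the primary immunogenicity set a result that the deviation could not have changed.

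**Conclusion.** The point holds as a small error in the elimination rule. For codes 1070, 1080, 1090 and 2080, the start of elimination falls one sample early whenever the affected injection shares a visit with a sample. At Visit 3 this follows from the SAP's own labelling. At Visits 5 and 7 it applies to code 1070 and depends on blood being drawn before the injection.

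The consequence is a modest loss of precision at Day 31: about 1% to 5% wider log-scale intervals in a group of 50 if 1 to 5 of its infants are affected, with that count assumed. No primary endpoint is touched and no bias is demonstrated. Minor severity.

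**What to change.** In section 4.2.3.1, take codes 1070, 1080, 1090 and 2080 out of the visit-of-occurrence rule and start their elimination at the first blood sample drawn after the affected injection:

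- Visit 1 deviation: from Day 31 onwards
- Visit 3 deviation: from Day 61 onwards
- Visit 5 or Visit 6 deviation: from the end-of-season sample

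Change the visit column of code 2080 from Visit 3 to Visits 5 and 7. Keep elimination at the visit of occurrence for codes 2090, 2100 and 2120, which describe the sample itself. If the programming already works this way, the text should say so.

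The cost is one sentence, one table cell and a small change to the elimination-code program. No new data are needed and trial conduct is unchanged.

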primary series and booster dose. The first *Bexsero* or *Nimenrix* dose will be administered at Day 1 (Visit 1) (in the groups receiving only *Bexsero* or *Nimenrix*, respectively). In the groups receiving only *Bexsero* or *Nimenrix*, the second dose will be at Day 61 (Visit 5). The first *Bexsero* or *Nimenrix* dose to be administered to the 1D and 2D RSV groups will be at Day 61 (Visit 5), following the 1 or 2 RSV vaccine doses, respectively. The second dose of *Bexsero* or *Nimenrix* in the 1D and 2D groups will be at Day 121 (Visit 6). Formulation buffer will be administered, when neither RSV vaccine nor comparator is scheduled, at the 5 vaccination visits (see Figure 1 and Table 1).

- In countries where *Synflorix* is used as a control, two doses will be administered IM with at least a 1 month interval between these primary doses. A booster dose will be administered IM in the second year of life at Visit 7. The first *Synflorix* dose will be administered at Day 31 (Visit 3) (in the group receiving only *Synflorix*). In the group receiving only *Synflorix*, the second dose will be at Day 61 (Visit 5). The first *Synflorix* dose to be administered to the 1D and 2D RSV groups will be at Day 61 (Visit 5), following the 1 or 2 RSV vaccine doses, respectively. The second dose of *Synflorix* in the 1D and 2D groups will be at Day 121 (Visit 6). Formulation buffer will be administered, when neither RSV vaccine nor comparator is scheduled, at the 5 vaccination visits (see Figure 1 and Table 1).
- In countries where *Menveo* is used as a control, two doses will be administered IM at least 3 months apart with the second dose in the second year of life at Visit 7. The first *Menveo* dose will be administered at Day 31 (Visit 3) (in the group receiving only *Menveo*). The first *Menveo* dose to be administered to the 1D and 2D RSV groups will be at Day 61 (Visit 5), following the 1 or 2 RSV vaccine doses, respectively. Since the second *Menveo* dose has to be administered in the second year of life at Visit 7, no administration will be performed at Day 121 (Visit 6). Formulation buffer will be administered, when neither RSV vaccine or comparator is scheduled, at the 4 vaccination visits (see Figure 1 and Table 1).

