4. ANALYSIS SETS

4.1. Definition

4.1.1. Exposed Set

The Exposed Set (ES) will include all subjects with at least one study vaccine administration documented.

- A safety analysis based on the ES will include all vaccinated subjects.
- An immunogenicity analysis will be conducted on the ES and will include all vaccinated subjects for whom immunogenicity data are available.

The ES analysis will be performed per treatment actually administered at Dose 1

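### Elimination code 1070 and the matching 4.1.3 bullets are not limited to RSV vaccine, so a site, route or volume error in a comparator or buffer injection removes RSV antibody results from the per-protocol set

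*SAP*

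**What the plan says.** Section 4.2.3.1 of the SAP lists code 1070 in two rows. The first reads "Subjects got vaccinated with the correct vaccine but containing a lower volume". The second covers a wrong study vaccine, a wrong or unknown site or route, and other departures in administration that the investigator specifies. Both rows apply at all visits and to the immunogenicity set. For code 1070, among others, "subjects will be eliminated from a specific visit (at which the condition is met) onwards".

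The PPS definition in section 4.1.3 is just as open. One of its bullets requires subjects "For whom the administration route and site of the vaccine was as according to protocol", with no product named.

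Other conditions in the same table are narrower. Code 1080 covers a "no-go temperature deviation for RSV vaccines only". Code 1090 reads "Expired vaccine administered (only applicable for RSV vaccine". One blood-sampling window under code 2090 reads "Number of days between dose 2 and visit 5 blood sample is outside [28-37 days] for RSV 2D group".

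In this SAP, study vaccine cannot mean RSV vaccine alone. By section 4.1.1 the Exposed Set "will include all subjects with at least one study vaccine administration documented", and control infants, who receive only comparator or buffer, could not otherwise belong to it.

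**The concern.** The immunogenicity endpoints measure the response to the RSV vaccine. Code 1070 lets errors in other products decide which RSV results enter the primary immunogenicity set. An infant in an RSV arm who had every RSV dose correctly, and then a comparator injection at the wrong site at Visit 5, leaves the Day 61 PPS although the Day 61 blood sample belongs to that same visit. The same infant given an expired or temperature-damaged comparator would stay in. The SAP gives no reason for treating these two cases differently.

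At stake are valid post-vaccination and end-of-season antibody results in pooled groups with a target of 50. Under section 5.2.1 the second analysis on the Exposed Set follows only when more than 10% of subjects with results are excluded in some group, so smaller losses go without that check.

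**Working it through.** The SAP states no figure to reproduce here. The check is a count of injections from Table 1, followed by a range of assumed error rates.

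**Step 1: which non-RSV injections can trigger the code.** Immunogenicity blood is taken at Screening, Day 31 (Visit 3), Day 61 (Visit 5) and the end of the first season (Visit 7) (SAP section 2).

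| Injection without RSV vaccine | Who receives it (Table 1) | PPS results removed |
|---|---|---|
| Visit 3 | 1D arms (buffer); control arms (buffer or comparator) | Day 31 onwards |
| Visit 5 | all arms in active-comparator countries | Day 61 and end of season |
| Visit 6 | all arms in Bexsero, Nimenrix and Synflorix countries | end of season |
| Visit 7 | all arms in active-comparator countries | end of season |

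No group is scheduled to receive RSV vaccine at Visits 5, 6 or 7. At Visits 3, 5 and 7 the sample removed includes the one taken at the same visit as the injection.

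**Step 2: injections per infant.** At Visits 5 and 6 there are 2 in Bexsero, Nimenrix and Synflorix countries, 1 in Menveo countries and 0 in Placebo countries. Counting Visit 7 as well gives 3, 2 and 0. The 1D and control arms have one further non-RSV injection at Visit 3.

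**Step 3: expected loss.** With an assumed deviation rate e per injection, and k independent injections, the proportion removed is 1 − (1 − e)^k. Multiplying by 50 gives infants per pooled group, if every infant in the group had k such injections.

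| e (assumed) | k = 1 | k = 2 | k = 3 |
|---|---|---|---|
| 0.5% | 0.25 | 0.5 | 0.75 |
| 1% | 0.5 | 1.0 | 1.5 |
| 2% | 1.0 | 2.0 | 2.9 |
| 3% | 1.5 | 3.0 | 4.4 |

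For example, at e = 3% and k = 2: 1 − 0.97² = 0.0591, and 0.0591 × 50 = 2.96.

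**Step 4: the 10% trigger.** If all 50 infants have results, 5 exclusions are exactly 10% and bring no second analysis; the sixth does. The chance of 6 or more from this cause alone is the upper tail of a binomial with n = 50 and the proportion from Step 3. For k = 2 it is under 0.1% at e = 0.5%, 1.4% at 2% and 7.3% at 3%. For k = 3 and e = 3% it is 27%.

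**Step 5: precision.** Losing 3 of 50 widens a log-titre interval by a factor of about √(50/47) = 1.03. Losing 5, the most that passes without the second analysis, gives √(50/45) = 1.05.

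**The case against.** The strongest defence is that nothing in the SAP is contradicted. Section 4.1.3 defines the PPS by correct administration of study vaccine, and code 1070 carries that out. Requiring the whole assigned regimen to be given correctly is a common, prespecified choice, and the authors, who wrote an RSV-only limit into codes 1080 and 1090, may have left it out of 1070 on purpose. Those two codes concern temperature and expiry, so they set no rule for site, route or volume. The endpoints are secondary and descriptive.

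Part of this stands: 4.1.3 and 4.2.3.1 agree with each other, and 1080 and 1090 serve only as a comparison. But a full-regimen PPS would not keep an infant who received an expired comparator, and it gives no reason why an injection should void the sample of its own visit.

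Three stronger readings are tempting, and the SAP does not support them.

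- That the results are deleted. They leave the PPS only. Section 4.1.1 provides for immunogenicity analysis on the Exposed Set, 5.2.1 requires it above 10% exclusion, and 5.2.1.1.1 plans an analysis on exposed subjects with negative RSV exposure status with no such condition.
- That the arms are biased against one another. Within a comparator country, Table 1 gives all three arms the same number of injections at each visit, and allocation takes account of country and comparator/placebo grouping, so the chance of exclusion is balanced by design. Placebo countries have no injections at Visits 5 to 7, so the PPS could shift in country mix, but no effect on a geometric mean is shown.
- That the injection is proven to have no effect. This is an inference. It is strong for a sample taken at the same visit, although the SAP does not give the order of sampling and injection. For an earlier comparator or buffer injection and the Visit 7 sample, it rests on these products not being RSV vaccines.

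**Conclusion.** The point holds as a matter of scope. As written, volume, site and route errors in comparator or buffer injections remove RSV antibody results from the PPS, including results from the same visit that the injection cannot plausibly affect.

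The size is modest: about 0.5 to 3 infants per 50 at an assumed 0.5% to 3% per injection with two injections. It is smaller where Menveo or Placebo is used, and larger if the Visit 7 injection, or the Visit 3 buffer in the 1D arms, is counted too. The per-50 figures are ceilings for a given k, because they treat every infant as having all k injections, and the mix of countries is not known. The rates are assumptions, since the SAP gives none. The change is worth making because it is cheap and the rule has no stated purpose for these endpoints.

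**What to change.** In section 4.2.3.1, limit the low-volume and site/route conditions of code 1070 to injections in which RSV vaccine was scheduled or given. Make the same change in the matching bullets of 4.1.3. Keep the wrong-study-vaccine condition for all products, so that RSV vaccine given in error or omitted still eliminates. State how the investigator-specified reason in the second 1070 row applies to comparator and buffer, so that a low-volume comparator does not return by that route.

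Add that an administration error eliminates only samples taken after that injection, not the sample of the same visit. This also settles the case of an RSV Dose 2 error at Visit 3, which at present removes the Day 31 result.

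The cost is SAP wording. Two consequences should be stated. Control infants would rarely be excluded for administration errors while RSV infants still would be; this difference already exists under 1080 and 1090. And the PPS would no longer certify full compliance with the comparator schedule. If the sponsor prefers the present scope, the SAP should say why 1070 extends to comparator and buffer when 1080 and 1090 do not.
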